#### **11. MEASUREMENT OF EFFECT**

#### **11.1** Antitumor Effect – Solid Tumors

For the purposes of this study, participants should be re-evaluated for response 8 weeks. After completing one year of treatment, re-evaluation should occur every 12 weeks. In addition to a baseline scan, confirmatory scans should also be obtained 4 (not less than 4) weeks following initial documentation of objective response.

Response and progression will be evaluated in this study using the new international criteria proposed by the Response Evaluation Criteria in Solid Tumors (RECIST) guideline (version 1.1) [*Eur J Ca* 45:228-247, 2009]. Changes in the largest diameter (unidimensional measurement) of the tumor lesions and the shortest diameter in the case of malignant lymph nodes are used in the RECIST criteria.

#### 11.1.1 Definitions

Evaluable for Target Disease response. Only those participants who have measurable disease present at baseline, have received at least one cycle of therapy, and have had their disease re-evaluated will be considered evaluable for target disease response. These participants will have their response classified according to the definitions stated below. (Note: Participants who exhibit objective disease progression prior to the end of cycle 1 will also be considered evaluable.)

Evaluable Non-Target Disease Response. Participants who have lesions present at baseline that are evaluable but do not meet the definitions of measurable disease, have received at least one cycle of therapy, and have had their disease re-evaluated will be considered evaluable for non-target disease. The response assessment is based on the presence, absence, or unequivocal progression of the lesions.

#### 11.1.2 Disease Parameters

Measurable disease. Measurable lesions are defined as those that can be accurately measured in at least one dimension (longest diameter to be recorded) as  $\geq 20$  mm by chest x-ray or  $\geq 10$  mm with CT scan, MRI, or calipers by clinical exam. All tumor measurements must be recorded in millimeters (or decimal fractions of centimeters).

Note: Tumor lesions that are situated in a previously irradiated area might or might not be considered measurable.

Malignant lymph nodes. To be considered pathologically enlarged and measurable, a lymph node must be  $\geq 15$  mm in short axis when assessed by CT scan (CT scan slice thickness recommended to be no greater than 5 mm). At baseline and in follow-up, only the short axis will be measured and followed.

Non-measurable disease. All other lesions (or sites of disease), including small lesions

(longest diameter <10 mm or pathological lymph nodes with  $\geq$ 10 to <15 mm short axis), are considered non-measurable disease. Bone lesions, leptomeningeal disease, ascites, pleural/pericardial effusions, lymphangitis cutis/pulmonitis, inflammatory breast disease, abdominal masses (not followed by CT or MRI), and cystic lesions are all considered non-measurable.

Note: Cystic lesions that meet the criteria for radiographically defined simple cysts should not be considered as malignant lesions (neither measurable nor non-measurable) since they are, by definition, simple cysts.

'Cystic lesions' thought to represent cystic metastases can be considered as measurable lesions, if they meet the definition of measurability described above. However, if noncystic lesions are present in the same participant, these are preferred for selection as target lesions.

Target lesions. All measurable lesions up to a maximum of 2 lesions per organ and 5 lesions in total, representative of all involved organs, should be identified as **target lesions** and recorded and measured at baseline. Target lesions should be selected on the basis of their size (lesions with the longest diameter), be representative of all involved organs, but in addition should be those that lend themselves to reproducible repeated measurements. It may be the case that, on occasion, the largest lesion does not lend itself to reproducible measurement in which circumstance the next largest lesion which can be measured reproducibly should be selected. A sum of the diameters (longest for non-nodal lesions, short axis for nodal lesions) for all target lesions will be calculated and reported as the baseline sum diameters. If lymph nodes are to be included in the sum, then only the short axis is added into the sum. The baseline sum diameters will be used as reference to further characterize any objective tumor regression in the measurable dimension of the disease.

Non-target lesions. All other lesions (or sites of disease) including any measurable lesions over and above the 5 target lesions should be identified as **non-target lesions** and should also be recorded at baseline. Measurements of these lesions are not required, but the presence, absence, or in rare cases unequivocal progression of each should be noted throughout follow up.

#### 11.1.3 Methods for Evaluation of Disease

All measurements should be taken and recorded in metric notation using a ruler, calipers, or a digital measurement tool. All baseline evaluations should be performed as closely as possible to the beginning of treatment and never more than 4 weeks before the beginning of the treatment.

The same method of assessment and the same technique should be used to characterize each identified and reported lesion at baseline and during follow-up. Imaging-based evaluation is preferred to evaluation by clinical examination unless the lesion(s) being followed cannot be imaged but are assessable by clinical exam. Clinical lesions. Clinical lesions will only be considered measurable when they are superficial (*e.g.*, skin nodules and palpable lymph nodes) and  $\geq 10$  mm in diameter as assessed using calipers (*e.g.*, skin nodules). In the case of skin lesions, documentation by color photography, including a ruler to estimate the size of the lesion, is recommended.

Chest x-ray. Lesions on chest x-ray are acceptable as measurable lesions when they are clearly defined and surrounded by aerated lung; however, CT is preferable.

Conventional CT and MRI. This guideline has defined measurability of lesions on CT scan based on the assumption that CT thickness is 5mm or less. If CT scans have slice thickness greater than 5 mm, the minimum size of a measurable lesion should be twice the slice thickness. MRI is also acceptable in certain situations (*e.g.* for body scans).

Use of MRI remains a complex issue. MRI has excellent contrast, spatial, and temporal resolution; however, there are many image acquisition variables involved in MRI, which greatly impact image quality, lesion conspicuity, and measurement. Furthermore, the availability of MRI is variable globally. As with CT, if an MRI is performed, the technical specifications of the scanning sequences used should be optimized for the evaluation of the type and site of disease. Furthermore, as with CT, the modality used at follow-up should be the same as was used at baseline and the lesions should be measured/assessed on the same pulse sequence. It is beyond the scope of the RECIST guidelines to prescribe specific MRI pulse sequence parameters for all scanners, body parts, and diseases. Ideally, the same type of scanner should be used and the image acquisition protocol should be followed as closely as possible to prior scans. Body scans should be performed with breath-hold scanning techniques, if possible.

PET-CT. At present, the low dose or attenuation correction CT portion of a combined PET-CT is not always of optimal diagnostic CT quality for use with RECIST measurements. However, if the site can document that the CT performed as part of a PET-CT is of identical diagnostic quality to a diagnostic CT (with IV and oral contrast), then the CT portion of the PET-CT can be used for RECIST measurements and can be used interchangeably with conventional CT in accurately measuring cancer lesions over time. Note, however, that the PET portion of the CT introduces additional data which may bias an investigator if it is not routinely or serially performed.

Ultrasound. Ultrasound is not useful in assessment of lesion size and should not be used as a method of measurement. Ultrasound examinations cannot be reproduced in their entirety for independent review at a later data and, because they are operator dependent, it cannot be guaranteed that the same technique and measurements will be taken from one assessment to the next. If new lesions are identified by ultrasound in the course of the study, confirmation by CT is advised.

#### 11.2 Response Criteria

#### 11.2.1 Evaluation of Target Lesions

Complete Response (CR): Disappearance of all target lesions. Any pathological lymph nodes (whether target or non-target) must have reduction in short axis to <10 mm.

Partial Response (PR): At least a 30% decrease in the sum of the diameters of target lesions, taking as reference the baseline sum diameters.

Progressive Disease (PD): At least a 20% increase in the sum of the diameters of target lesions, taking as reference the smallest sum on study (this includes the baseline sum if that is the smallest on study). In addition to the relative increase of 20%, the sum must also demonstrate an absolute increase of at least 5 mm. (Note: the appearance of one or more new lesions is also considered progressions).

Stable Disease (SD): Neither sufficient shrinkage to qualify for PR nor sufficient increase to qualify for PD, taking as reference the smallest sum diameters while on study.

11.2.2 Evaluation of Non-Target Lesions

Complete Response (CR): Disappearance of all non-target lesions and normalization of tumor marker level. All lymph nodes must be non-pathological in size (<10 mm short axis).

Note: If tumor markers are initially above the upper normal limit, they must normalize for a patient to be considered in complete clinical response.

Non-CR/Non-PD: Persistence of one or more non-target lesion(s) and/or maintenance of tumor marker level above the normal limits.

Progressive Disease (PD): Appearance of one or more new lesions and/or *unequivocal progression* of existing non-target lesions. *Unequivocal progression* should not normally trump target lesion status. It must be representative of overall disease status change, not a single lesion increase.

Although a clear progression of "non-target" lesions only is exceptional, the opinion of the treating physician should prevail in such circumstances, and the progression status should be confirmed at a later time by the review panel (or Principal Investigator).

#### 11.2.3 Evaluation of New Lesions

The finding of a new lesion should be unequivocal (i.e. not due to difference in scanning technique, imaging modality, or findings thought to represent something other than tumor (for example, some 'new' bone lesions may be simply healing or

flare of pre-existing lesions). However, a lesion identified on a follow-up scan in an anatomical location that was not scanned at baseline is considered new and will indicate PD. If a new lesion is equivocal (because of small size etc.), follow-up evaluation will clarify if it truly represents new disease and if PD is confirmed, progression should be declared using the date of the initial scan on which the lesion was discovered.

#### 11.2.4 Evaluation of Best Overall Response

The best overall response is the best response recorded from the start of the treatment until disease progression/recurrence (taking as reference for progressive disease the smallest measurements recorded since the treatment started). The patient's best response assignment will depend on the achievement of both measurement and confirmation criteria.

Target Lesions	Non-Target Lesions	New Lesions	Overall Response	Best Overall Response when Confirmation is Required*		
CR	CR	No	CR	>4 wks Confirmation**		
CR	Non-CR/Non- PD	No	PR			
CR	Not evaluated	No	PR	> 4 water Confirmention **		
PR	Non-CR/Non- PD/not evaluated	No	PR	≥4 wks Confirmation**		
SD	Non-CR/Non- PD/not evaluated	No	SD	Documented at least once ≥4 wks from baseline**		
PD	Any	Yes or No	PD			
Any	PD***	Yes or No	PD	no prior SD, PR or CR		
Any	Any	Yes	PD			

 
See RECIST 1.1 manuscript for further details on what is evidence of a new lesion.
 
Only for non-randomized trials with response as primary endpoint.
 
In exceptional circumstances, unequivocal progression in non-target lesions may be accepted as disease progression.
 
						
Note : Participants with a global deterioration of health status requiring discontinuation of treatment without objective evidence of disease progression at that time should be reported as " symptomatic deterioration ." Every effort should be made to document the objective progression even after discontinuation of treatment.						

## For Participants with Measurable Disease (i.e., Target Disease)

## For Participants with Non-Measurable Disease (*i.e.*, Non-Target Disease)

Non-Target Lesions	New Lesions	Overall Response
--------------------	-------------	------------------

CR	No	CR		
Non-CR/non-PD	No	Non-CR/non-PD*		
Not all evaluated	No	not evaluated		
Unequivocal PD	Yes or No	PD		
Any	Yes	PD		
* 'Non-CR/non-PD' is preferred over 'stable disease' for non-target disease since SD is increasingly used as an endpoint for assessment of efficacy in some trials so to assign this category when no lesions can be measured is not advised				

#### 11.2.5 Duration of Response

Duration of overall response: The duration of overall response is measured from the time measurement criteria are met for CR or PR (whichever is first recorded) until the first date that recurrent or progressive disease is objectively documented (taking as reference for progressive disease the smallest measurements recorded since the treatment started, or death due to any cause. Participants without events reported are censored at the last disease evaluation).

Duration of overall complete response: The duration of overall CR is measured from the time measurement criteria are first met for CR until the first date that progressive disease is objectively documented, or death due to any cause. Participants without events reported are censored at the last disease evaluation.

Duration of stable disease: Stable disease is measured from the start of the treatment until the criteria for progression are met, taking as reference the smallest measurements recorded since the treatment started, including the baseline measurements.

## 11.2.6 Progression-Free Survival

Progression-Free Survival (PFS) is defined as the time from randomization (or registration) to the earlier of progression or death due to any cause. Participants alive without disease progression are censored at date of last disease evaluation.

Overall Survival: Overall Survival (OS) is defined as the time from randomization (or registration) to death due to any cause, or censored at date last known alive.

Progression-Free Survival: Progression-Free Survival (PFS) is defined as the time from randomization (or registration) to the earlier of progression or death due to any cause. Participants alive without disease progression are censored at date of last disease evaluation.

Time to Progression: Time to Progression (TTP) is defined as the time from randomization (or registration) to progression, or censored at date of last disease evaluation for those without progression reported.

# 12. DATA REPORTING / REGULATORY REQUIREMENTS

Adverse event lists, guidelines, and instructions for AE reporting can be found in Section 7.0 (Adverse Events: List and Reporting Requirements).

# 12.1 Data Reporting

# 12.1.1 Method

The Office of Data Quality (ODQ) will collect, manage, and perform quality checks on the data for this study.

# 12.1.2 Responsibility for Data Submission

Investigative sites within DF/HCC or DF/PCC are responsible for submitting data and/or data forms to the Office of Data Quality in accordance with DF/HCC SOPs.

# 12.2 Data Safety Monitoring

The DF/HCC Data and Safety Monitoring Committee (DSMC) will review and monitor toxicity and accrual data from this study. The committee is composed of clinical specialists with experience in oncology and who have no direct relationship with the study. Information that raises any questions about participant safety will be addressed with the Overall PI and study team.

The DSMC will review each protocol up to four times a year or more often if required to review toxicity and accrual data. Information to be provided to the committee may include: up-to-date participant accrual; current dose level information; DLT information; all grade 2 or higher unexpected adverse events that have been reported; summary of all deaths occurring with 30 days of intervention for Phase I or II protocols; for gene therapy protocols, summary of all deaths while being treated and during active follow-up; any response information; audit results, and a summary provided by the study team. Other information (e.g. scans, laboratory values) will be provided upon request.

# **13. STATISTICAL CONSIDERATIONS**

# 13.1 Study Design/Endpoints

This is a phase II study designed to evaluate the efficacy of the combination of EGF816 and gefitinib in the first-line treatment of EGFR-mutant non-small cell lung cancer. The primary endpoint is proportion of patients free from progression at 9 months. The study is designed as a Simon two-stage study. The null hypothesis is that EGF816 does not add any benefit to gefitinib monotherapy, with the assumption that the median PFS for gefitinib monotherapy is 9 mo, in other words 50% of patients will be free from progression at 9 months. The study is designed to have 80% power at the 0.05 significance level to show that the combination regimen of gefitinib plus EGF816 increases the proportion of progression-free patients at 9 months to 73% using a

one-sided binomial test. The total study size is 36 patients. 11 patients will be enrolled in the first stage of the study, with a planned second stage of 25 patients if at least 7 patients in the first-stage are progression-free at nine month. The rejection criteria for the null would be having 23 patients who are progression-free by 9 months. Based on our prior experience with first-line treatment of pateints with EGFR mutant NSCLC, we do not expect any patients to be lost to follow-up or unevaluable prior to the 9 month timepoint.

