# 2.3 Gefitinib

Gefitinib is an oral first-generation EGFR inhibitor which reversibly inhibits the kinase activity of wild-type and certain activating mutations of EGFR, preventing autophosphorylation of tyrosine residues associated with the receptor, thereby inhibiting further downstream signaling and blocking EGFR-dependent proliferation. Gefitinib's binding affinity for EGFR exon 19 deletion or exon 21 point mutation L858R mutations is higher than its affinity for the wild-type EGFR. Gefitinib also inhibits IGF and PDGF-mediated signaling at clinically relevant concentrations; inhibition of other tyrosine kinase receptors has not been fully characterized.

Gefitinib is approved for the first-line treatment of EGFR-mutant NSCLC in the United States, Europe and Asia. The IPASS study was a randomized, multicenter, open-label trial conducted in patients with metastatic adenocarcinoma histology NSCLC receiving first-line treatment. Patients were randomized (1:1) to receive gefitinib 250 mg orally once daily or up to 6 cycles of carboplatin/paclitaxel. The efficacy outcomes included progression-free survival (PFS) and objective response rate (ORR) as assessed by BICR.

The subset population consisted of 186 of 1217 patients (15%) determined to be EGFR positive and had radiographic scans available for a retrospective assessment by BICR. In this subset, there were 88 gefitinib-treated patients and 98 carboplatin/paclitaxel-treated patients. Demographic and baseline characteristics of this subset were a median age of 59 years, age 75 years or older (7%), age less than 65 (70%), Asian (100%), female (83%), never smokers (96%), adenocarcinoma histology (100%), and PS 0-1 (94%).

The median duration of treatment for gefitinib-treated patients was 9.8 months. The hazard ratio for PFS favored the gefitinib-treated patients [HR of 0.54 (95% CI: 0.38, 0.79)] with a median PFS of 10.9 months for the gefitinib-treated patients and 7.4 months for the carboplatin/paclitaxel-treated patients as assessed by BICR. In addition, the objective response rate was 67% (95% CI: 56, 77) for gefitinib-treated patients and 41% (95% CI: 31, 51) for carboplatin/paclitaxel-treated patients based on BICR assessment. The median duration of response was 9.6 months for gefitinib-treated patients and 5.5 months for carboplatin/paclitaxel-treated patients.

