# **13.2** Sample Size, Accrual Rate and Study Duration

As stated above, 11 patients will be enrolled in the first stage of the study, with a planned second stage of 25 patients if at least 7 patients in the first-stage are progression-free at nine months. The null will be rejected and the study deemed positive if at least 23 total patients are progression-free at 9 months.

We expect to accrue approximately 10-15 patients/year, therefore assuming the study advances to the second stage and that there may be a brief pause in enrollment between the first and second stage (to allow for patients to reach the 9 month endpoint), will complete accrual for the study within 3 years. Final data for the primary endpoint will be mature within 4 years.

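### The 50% null stands for gefitinib alone but rests on an uncited 9-month median; at the protocol's own 10.9 months, a regimen no better than gefitinib passes the 23/36 rule more often than 5%, so reaching 23 supports only more than 50% at 9 months

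*Combined protocol and SAP*

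**What the plan says.** Section 13.1 frames the null hypothesis as EGF816 adding nothing to gefitinib monotherapy. It turns this into a number "with the assumption that the median PFS for gefitinib monotherapy is 9 mo". From that median it reads off the null proportion directly: "in other words 50% of patients will be free from progression at 9 months". No reference or derivation accompanies the 9 months.

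The operating characteristics follow: "The study is designed to have 80% power at the 0.05 significance level", for a regimen that "increases the proportion of progression-free patients at 9 months to 73"%, by a "one-sided binomial test". "The total study size is 36 patients": 11 in stage 1, then a "planned second stage of 25 patients if at least 7 patients in the first-stage are progression-free at nine months". Section 13.2 calls the study positive once 23 patients in total are progression-free at 9 months.

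Section 2.3 reports a "median PFS of 10.9 months for the gefitinib-treated patients", assessed by blinded independent central review (BICR), among 88 EGFR-positive first-line patients on gefitinib. The other gefitinib durations there are not PFS: treatment duration 9.8 months and duration of response 9.6 months. The 9 to 13 months in section 2.1 refers to osimertinib and other third-generation inhibitors.

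**The concern.** In a single-arm trial the fixed benchmark is the comparator. Because the null is about gefitinib and not about an abstract 50%, rejecting it reads as evidence that EGF816 adds benefit. That inference is only as good as the equation of gefitinib with 50% at 9 months.

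Any gefitinib median above 9 months means that more than half of gefitinib patients are progression-free at 9 months, whatever the shape of the curve. The rule then passes a regimen with no added benefit more often than the nominal 5%. The protocol's own background figure is above 9 months, and nothing reconciles the two. At stake is what 23, 24 or 25 successes would allow the trial to conclude.

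**Working it through.** **Inputs.** Sections 13.1 and 13.2: n1 = 11, continue if at least 7; n2 = 25; positive if at least 23 of 36; null 0.50; alternative 0.73. Section 2.3: gefitinib median PFS 10.9 months. Assumption, not in the documents: the shape of the PFS curve (exponential first, then Weibull).

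**Formula.** For a true 9-month proportion p,

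P(positive) = Σ over x = 7 to 11 of P(X1 = x) × P(X2 ≥ 23 − x), with X1 ~ Bin(11, p) and X2 ~ Bin(25, p).

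**Step 1. The plan's own figures.** At p = 0.50 the terms for x = 7, 8, 9, 10 and 11 are 0.0185, 0.0171, 0.0093, 0.0027 and 0.0003, which sum to 0.048. At p = 0.73 the sum is 0.811. Both meet the stated 5% and 80%. The arithmetic is sound for a 50% null.

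**Step 2. Other gefitinib medians.** With exponential PFS and median m months, p0 = 0.5^(9/m). For m = 10.9, 9/10.9 = 0.826 and p0 = 0.5^0.826 = 0.564.

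| Gefitinib median (months) | p0 at 9 months | P(pass stage 1) | P(positive) |
|---|---|---|---|
| 9 | 0.500 | 0.274 | 0.048 |
| 9.5 | 0.519 | 0.318 | 0.073 |
| 10 | 0.536 | 0.361 | 0.104 |
| 10.5 | 0.552 | 0.403 | 0.141 |
| 10.9 | 0.564 | 0.435 | 0.174 |

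Section 1.2 states the endpoint at 39 weeks. Using 39 weeks (8.97 months) in place of 9 months changes the last figure only to 0.177.

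**Step 3. Curve shape.** With a Weibull curve of shape k and median 10.9 months, p0 = 0.5^((9/10.9)^k).

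| k | p0 | P(positive) |
|---|---|---|
| 0.8 | 0.552 | 0.140 |
| 1.0 | 0.564 | 0.174 |
| 1.2 | 0.576 | 0.212 |
| 1.5 | 0.594 | 0.274 |

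The size depends on the shape; the direction does not.

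**Step 4. What each result excludes.** The stage-adjusted one-sided 95% lower bound for r successes is the p at which the formula above, with r in place of 23, equals 0.05.

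| Successes of 36 | Observed proportion | Lower bound |
|---|---|---|
| 23 | 0.639 | 0.502 |
| 24 | 0.667 | 0.526 |
| 25 | 0.694 | 0.552 |
| 26 | 0.722 | 0.579 |

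All four exclude 50%. Results of 23 to 25 do not exclude 0.564.

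**The case against.** The 9 months is declared openly as an assumption, and the design is right for it. A reader might infer that the trial's real type I error is 17%. That would require 10.9 months to be the true gefitinib median for the patients enrolled here, and the documents do not establish this:

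- **Different population.** The 10.9 months comes from a retrospective subset (186 of 1217 patients, EGFR-positive and with scans available) that was 100% Asian, 83% female, 96% never-smokers and 94% PS 0-1, read centrally. This trial admits ECOG up to 2, one prior line of chemotherapy or immunotherapy, and other sensitizing mutations by agreement (sections 3.1.3, 3.1.6 and 3.1.10), and specifies no blinded central review. A lower benchmark may be defensible.
- **Sampling error.** The documents give no interval for the 10.9 months. Assuming exponential PFS and 50 to 88 events among the 88 patients, 10.9 × exp(±1.96/√d) gives 8.3 to 14.4 months at d = 50 and 8.8 to 13.4 at d = 88. On that assumption 9 months is compatible with the figure.
- **Incomplete text.** Some pages were removed before this review and a figure in section 2.3 is not shown, so another gefitinib PFS result could exist. Section 2.1 also cites other first-line work that was not available here.

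A reader might also infer that the success threshold should rise to 26/36. That follows only if the benchmark is exactly 56.4%. The error at 26 is then 0.035, but power at 73% falls to 0.589, and at Weibull shape 1.5 the error at 26 is 0.073. The documents do not support fixing that number.

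These points stand against a claim that the 5% is wrong. They do not supply the missing justification: the protocol makes none of these arguments, and its null is still worded as a comparison with gefitinib.

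**Conclusion.** The concern holds as a limit on the conclusion, not as an error in the design. The 7/11 then 23/36 rule controls error at 0.048 against a 50% null. Read as the protocol words it, against gefitinib, the chance of a false positive is 0.073 to 0.174 for medians of 9.5 to 10.9 months under exponential PFS, and 0.14 to 0.27 at 10.9 months across Weibull shapes 0.8 to 1.5. These are sensitivity figures conditional on the benchmark and the curve. They do not estimate the trial's actual error rate.

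What follows without a curve assumption is narrower: 23 of 36 shows that more than 50% are progression-free at 9 months, with a lower bound of only 0.502. Whether that is better than gefitinib depends on a benchmark the protocol has not justified.

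**What to change.** Keep the 36 patients, the two stages and the 23/36 rule.

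1. In section 13.1, justify the 9-month gefitinib median for the enrolled population with a source, or reconcile it with the 10.9 months in section 2.3.
2. In the same section, tabulate the probability of a positive result for gefitinib medians from 9 to 10.9 months, naming the curve assumption and giving the range over shapes.
3. Reword the null in 13.1 and the conclusion in 13.2 together, so that reaching 23/36 supports a proportion above 50% at 9 months. Changing only the conclusion would leave a rejected null whose denial could not be claimed.
4. Report the stage-adjusted one-sided 95% lower bound with the result, and claim benefit over gefitinib only if it exceeds the benchmark justified under item 1. Do not fix 26/36 as a second success threshold.

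The cost is wording and a short table. Sample size, conduct and patient management are unchanged. The downside is a weaker claim for borderline results: against a 56.4% benchmark, 23 to 25 successes would not support added benefit over gefitinib.
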